
Specific Aim 2: To test whether these interventions narrow the existing Black/non-Black inequity in postpartum outcomes such as blood pressure control and severe hypertension.

Aim 2 Analytic Approach: Given racial disparities in postpartum outcomes and hypothesized heterogeneity of intervention effect, we plan for two pre-specified subgroup analysis in (1) standard care only (N=250) (2) Black participants only (N=500). The first subgroup analysis aims to assess racial disparities in postpartum outcomes without intervention where Black/non-Black will be the main effect of interests. The second subgroup analysis aims to reassess intervention effects observed in Aim 1 but within Black participants. To test the hypothesis of the interventions narrowing racial inequity,

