we will use the overall cohort (N=1000) and additionally include the interaction between Black/Non-Black and the intervention effects (two main effects + one interaction effects) on top of all models in Aim 1. Missing data will be handled in the similar fashion as Aim 1. **Power and Sample Size Considerations (All Aims):** For Aim 1, power consideration is conducted in the setting of two group comparisons with sample size of N=250 (N=75 for Aim 3) in the standard care group and N=500 (N=150 for Aim 3) for each individual intervention instead of in the setting of 2x2 factorial design with N=1000 (N=300 for Aim 3) because the effect size of F-statistics for continuous outcomes and chi-square statistics for binary outcomes is not clinically interpretable. Review of institutional data found that 10.2% of patients with HDP at delivery experience sustained severe hypertension within the first 6 weeks postpartum and these patients have a mean SBP of 138 (SD 17.2) and mean DBP of 83 (SD 11.9). We will have 80% power to detect a minimum of 0.22 standardized reduction in SBP and DBP (a small effect by Cohen's nomenclature¹⁰³) which corresponds to reduction in SBP from 138 to 134 mmHg and DBP from 83 to 80 mmHg. Additionally, we will have 80% power to detect 57% reduction in sustained severe hypertension. Minimum detectable effect sizes for selected secondary outcomes in Aim 1 and the primary outcome for Aim 3 are provided (Table 6). For Aim 3, we will have 80% power to detect a minimum of 0.4 standardized difference in cardiovascular outcomes (a medium effect by Cohen's nomenclature), which corresponds to an increase of lateral e' from 11.7 to 13.1. For Aim 2, power justification is conducted based on N=300 using analysis of variance (ANOVA) for the interaction terms between race and interventions effects (with 3 degree of freedom) for the SBP and DBP primary outcomes. The minimum detectable F-statistics for the overall interaction term is 0.19 which is small-to-medium effect by Cohen's nomenclature. The power consideration does not consider adjusting covariates and thus is conservative since inclusion of adjusting covariates will improve the power of the study.

Table 6: Minimum detectable Relative Risk (alpha=0.05, 80% power, N=1000)

Outcome	Baseline	Minimum Detectable RR or Effect Size
Mean systolic blood pressure (SD)	138 (17.2)	4
Mean diastolic blood pressure (SD)	83 (11.9)	3
Sustained severe blood pressure (%)	10%	43%
Postpartum visit attendance (%)	40%	63%

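### Aim 2 asks whether each intervention narrows the Black/non-Black gap, but the only Aim 2 test the plan names ignores direction and does not attribute a change to either intervention

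*Combined protocol and SAP*

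**What the plan says.** Specific Aim 2 is directional: "To test whether these interventions narrow the existing Black/non-Black inequity in postpartum outcomes". The Aim 2 Analytic Approach repeats this ("To test the hypothesis of the interventions narrowing racial inequity") and says "we will use the overall cohort (N=1000" participants) and "additionally include the interaction between Black/Non-Black and the intervention effects (two main effects + one interaction effects") on top of the Aim 1 models. Those models hold a binary variable for monitoring, a binary variable for the goal, and their product. Aim 2 therefore adds race x monitoring, race x goal and a three-way term. For Aim 1 the plan says what a negative coefficient means; for the race terms it names no contrast, decision test or sign.

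The section on power and sample size is the only place that names an Aim 2 test: "analysis of variance (ANOVA) for the interaction terms between race and interventions effects (with 3 degree of freedom"), for SBP and DBP. It adds "For Aim 2, power justification is conducted based on N=300" and "The minimum detectable F-statistics for the overall interaction term is 0.19".

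Two subgroup analyses are also prespecified: the racial difference within standard care (N=250), and the intervention effects within Black participants (N=500).

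**The concern.** The hypothesis has a direction and concerns each intervention. A joint F test of three terms has no direction and rejects for narrowing, for widening, or for a three-way pattern that answers neither question. A significant result would not by itself support the statement that remote monitoring, or tight control, reduces the inequity.

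Reading the fitted coefficients instead does not settle it. Aim 1 interprets its main effects as each intervention alone against standard care, which implies 0/1 coding. With that coding and the three-way term in the model, race x monitoring is the change in gap in the standard-goal half of the trial only.

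At stake are the interpretability of the disparity result and, in some scenarios, the chance of detecting a real narrowing.

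**Working it through.** **Inputs.** SD of SBP 17.2 mmHg (power paragraph). Four equal arms (Interventions). 50% Black (Enrollment and Feasibility, stated as an aim). Alpha 0.05 and 80% power (Table 6 title, assumed to apply to Aim 2, which states neither). Two-sided 1-df tests (assumed). This gives eight race-by-arm cells, 125 each at N=1000.

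**The plan's figure.** For a 3-df F test with noncentrality λ = N·f² and N − 8 error df, 80% power at N=300 needs λ = 11.05, so f = √(11.05/300) = 0.192. At f = 0.19, power is 79.1%. The stated 0.19 is therefore reproduced, but as Cohen's f rather than an F-statistic. At N=1000 the same test needs f = 0.105.

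**In mmHg.** Let δ be the change in the Black minus non-Black mean between the two levels of one intervention, averaged over the other. If all the heterogeneity lies in that contrast, f = δ/(4·SD). At N=300, 4 × 0.192 × 17.2 = 13.2 mmHg.

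**Marginal contrast against omnibus, N=1000.**
- SE(δ) = SD·√(4/250) = 0.1265 SD = 2.18 mmHg.
- 1 df: 80% power needs λ = 7.86, so δ = √7.86 × 2.18 = 6.1 mmHg.
- 3 df: 80% power needs λ = 10.95, so δ = √10.95 × 2.18 = 7.2 mmHg, 18% larger. At λ = 7.86 its power is 64%.
- Bonferroni over two contrasts: 1-df power at 6.1 mmHg falls to 71%. The detectable change becomes (2.241 + 0.842) × 2.18 = 6.7 mmHg.

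**If the second intervention also shifts the gap** by r times the first, 3-df λ = 7.86 × (1 + r²). The first contrast stays at 80%.

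| r | λ | 3-df power |
|---|---|---|
| 0 | 7.86 | 64% |
| 0.5 | 9.83 | 75% |
| 0.65 | 11.19 | 81% |
| 1 | 15.73 | 93% |

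**Direction.** In 6,000 simulated trials at N=1000, the 3-df test rejected in 64.4% under narrowing and 64.2% under widening of the same size.

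**The 0/1-coded coefficient.** Race x monitoring at the standard goal uses four cells of 125: SE = SD·√(4/125) = 0.179 SD = 3.08 mmHg. The noncentrality halves to 3.93, so power at 6.1 mmHg is 51%.

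**The case against.** Four arguments favour the plan.

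1. **The power comparison depends on the scenario.** The plan expects both interventions to work, singly and together. The omnibus loses clearly only when one intervention carries the whole change; it overtakes the unadjusted contrast when the second effect is about 0.65 of the first. If the gap changes only in the combined arm, by 0.5 SD, omnibus λ = 0.75 × 0.25/0.016 = 11.7 (83% power) and each marginal λ = 0.0625/0.016 = 3.9 (51%). This stands. A reader might infer that the omnibus is generally weaker, or that Aim 2 has only 64% power. The documents support neither: at its stated effect and N=300 the planned test has about 79%.

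2. **The decision test is inferred.** The 3-df ANOVA appears only in the power paragraph. A reader might infer that its p-value decides Aim 2, but the analysis text does not say so. This also stands, and it leaves Aim 2 with either a sign-blind test or no stated test. The same edit repairs both.

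3. **Direction can be recovered** from the coefficients and subgroup analyses. This stands only in part. The standard-care subgroup gives the baseline gap, and the Black-only analysis gives effects in one group; neither estimates a change in the gap. The coefficients carry signs, but as coded they answer for one half of the trial.

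4. **Omnibus-first testing limits multiplicity.** That is a recognised strategy, but the plan names no follow-up contrasts for it to protect. A two-sided 1-df test also rejects for widening; the difference is that its single estimate shows the sign.

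**Conclusion.** The point holds as a mismatch between hypothesis and test. The one test named for Aim 2 cannot distinguish narrowing from widening or say which intervention is responsible, and the analysis text supplies no contrast or sign rule. This does not depend on any power figure.

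The power consequence is conditional. With the change confined to one intervention, the 3-df test has 64% power against 80% for the marginal contrast tested alone at 0.05, or 71% after Bonferroni over two. With equal narrowing from both, the omnibus has 93% against 80% for each contrast. The 51% for the 0/1-coded coefficient assumes that coding, which the Aim 1 text implies but does not state.

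All N=1000 figures assume eight equal cells, SD 17.2, a blood pressure value for all 1,000 participants and no covariate adjustment. The power statement needs rewriting in any case: it uses N=300, the number given for Aim 3, while the analysis uses N=1000, and it labels a Cohen's f as an F-statistic.

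**What to change.** In the Aim 2 Analytic Approach, name two marginal 1-df contrasts as the Aim 2 tests:

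- the change in the Black minus non-Black mean with remote against provider monitoring, averaged over goals;
- the same change with tight against standard goal, averaged over monitoring.

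State that a negative change means narrowing, given a positive gap under standard care. Report each contrast in mmHg with a 95% CI. State a multiplicity rule, including whether it spans SBP and DBP as well as the two contrasts. Keep the 3-df test and the three-way term as supportive.

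Replace the Aim 2 power statement with the detectable change in the SBP gap at N=1000 and 50% Black: about 6.1 mmHg per contrast unadjusted, or 6.7 mmHg with Bonferroni over two.

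The cost is SAP wording and the contrast statements; no further participants or data are needed. The downsides are the multiplicity penalty (80% to 71% for two contrasts) and less power than the omnibus when both interventions shift the gap.

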We propose a comprehensive management program for postpartum patients with HDP who are at risk for severe maternal morbidity and mortality. Our program will emphasize three key components: 1) self-monitoring of blood pressures with app-based reporting connected to our electronic health record, 2) blood pressure management directed by a program navigator with guideline and physician support and 3) facilitated transitions of care to primary care clinicians for hypertension management. We will randomize 1400 patients with HDP on postpartum day one with follow up through 3 months postpartum. Primary outcome will be blood pressure control at 2 weeks postpartum. Secondary outcomes include identification and treatment of severe blood pressures, severe maternal morbidity, postpartum and primary care visit attendance, and multiple patient-reported outcome measures. All outcomes will be stratified by race (Black and non-Black) to evaluate disparities and by tight versus usual blood pressure control to evaluate the impact of strict postpartum blood pressure control on outcomes. We hypothesize that a comprehensive postpartum HDP management program will improve hypertension control for all patients and reduce disparities that affect Black patients, and that stricter blood pressure control will be associated with fewer adverse outcomes.

OBJECTIVE

Specific Aim 1: To assess whether augmented remote blood pressure monitoring and tight blood pressure control, both individually and in combination, improve blood pressure control and the frequency of severe hypertension in the first 2 weeks postpartum.

Specific Aim 2: To test whether these interventions narrow the existing Black/non-Black inequity in postpartum outcomes such as blood pressure control and severe hypertension.

ELIGIBILITY CRITERIA

Inclusion Criteria

1. Age ≥ 18 years
2. Diagnosed with a Hypertensive Disorder of Pregnancy (HDP), which includes chronic hypertension, preeclampsia, gestational hypertension, HELLP Syndrome (Hemolysis, Elevated Liver enzymes, Low Platelets), or eclampsia (O10, O11, O13, O14, O15, O16)

Exclusion Criteria

1. Not able or willing to receive electronic surveys
2. Deemed inappropriate for study enrollment by bedside nurse
3. Non-English speaking
4. Discharge on postpartum day 6 or greater
5. Contraindication to ACOG-recommended hypertension control (i.e. chronic kidney disease, stroke)

SCREENING

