Weeks 3-6 after delivery	
 ▶ Check blood pressures once daily ▶ Record BPs daily in MyHealth ▶ Seek urgent care (triage, ED) for sustained severe HTN or symptoms 	
 ▶ Receive BPs notifications weekly ▶ Adjust antihypertensive medications based on sections (C) and (D) below
Communication with obstetric clinicians		
 ▶ Send updates on HTN management at weeks 2, 4, and 6 ▶ Document medication changes in EStar ▶ Send updates to non-VUMC obstetric clinicians with any antihypertensive medication changes
Care Handoffs	
 ▶ Schedule postpartum visit at 4-6 weeks ▶ Schedule a visit with a primary care clinician or cardiologist at month 3 	
 ▶ Ensure that postpartum visits are scheduled by 4-6 weeks ▶ Ensure that primary care or cardiology visits are scheduled at month 3 ▶ Remind patients about all visits

Blood pressure Control

(C) *Standard Blood Pressure Control*: Blood pressure targets will be <150 mmHg systolic and <100 mmHg diastolic consistent with current postpartum recommendations from ACOG. Blood pressure notifications for the HTN program navigator will reflect these parameters and medications will be initiated or titrated to meet these goals. See Appendix J for specifics on management and Appendix L for recommended medication regimens

(D) *Tight Blood Pressure Control*: Blood pressure targets will be <140 mmHg systolic and <90 mmHg diastolic. Blood pressure notifications for the HTN program navigator will reflect these parameters and medications will be initiated or titrated to meet these goals. See Appendix K for specifics on management and Appendix L for recommended medication regimens.

- ▶ **Survey 2** (6-weeks after delivery): Participants will receive the survey via text web-link or email link. Survey 2 asks questions about the participant's experience managing hypertension after delivery, the Mothers On Respect Index (MORI) and the Communication Assessment Tool geared towards postpartum care, the PROMIS Bank v1.0 Anxiety (adaptive) survey, the PROMIS Bank v1.0 Depression (adaptive) survey, the PROMIS Bank v2.0 Instrumental Support (adaptive) survey. We estimate that this survey will take 20 minutes to complete. Participants will receive a \$20 gift card for completion of this survey.

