Primary care visit attendance (%)	10%	43%
Diastolic dysfunction: Mean early diastolic filling or e' (SD)	11.7 (3.1)	1.24

DATA AND SAFETY MONITORING

Data will be entered directly into the Research Electronic Data Capture (REDCap) site, a secure web platform for building and managing online databases and surveys with flexible design of electronic CRFs. REDCap is compliant with the Health Insurance Portability and Accountability Act and includes password protection. REDCap maintains records of all changes made to databases so that investigators can identify deleted data and changes made. Each person accessing REDCap has an individual ID for security tracking and to prevent unauthorized access to data. Data can be exported to common statistical analysis packages (e.g., SAS, R, and Stata) and protected health information removed. Several internal quality checks are available in REDCap including: automatic range checks for numeric variables and creation of automatic data reports that help identify data that appears inconsistent, incomplete, or inaccurate. Every two weeks, a separate clinical trials associate assigned to support the study will audit 3 randomly selected charts to ensure that data have been entered correctly and for continuous process improvement. After obtaining informed consent, a copy of the consent form will be sent to participants via email or text and all information retained in the REDCap database. The REDCap database is encrypted and can only be accessed by research personnel with appropriate clearance.

For this study, an adverse event (AE) is defined as any untoward medical occurrence associated with the study, whether or not considered intervention- or procedure-related. An AE can therefore be any undesirable or unintended sign, symptom, laboratory testing or diagnostic imaging finding, or disease temporally associated with participation in the study, without any judgement about causality. The determination of the relationship between the AE and the study procedures must be made by the PI or their designee. This definition will also include changes in the participant medical status that may be related to the study procedures. Maternal medical conditions that are present prior to consent can be considered as baseline and not reported as AEs. However, if the participant's condition deteriorates at any time during the study, it will be recorded as an AE.

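### Table 6 gives detectable decreases for both attendance outcomes, which the programme is meant to increase, and its binary entries behave as odds ratios, not the relative risks in the title

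*Combined protocol and SAP*

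**What the plan says.** Table 6, in the power section, is titled "Minimum detectable Relative Risk (alpha=0.05, 80% power, N=1000", and its last column is headed "Minimum Detectable RR or Effect Size". It has three binary rows: sustained severe blood pressure (10%, 43%), postpartum visit attendance (40%, 63%) and "Primary care visit attendance" (10%, 43%).

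The accompanying text interprets only the first: "we will have 80% power to detect 57% reduction in sustained severe hypertension". Since 1 − 0.43 = 0.57, the entry is a ratio below 1. No other reading is offered for the attendance rows. The text also fixes the comparison: "power consideration is conducted in the setting of two group comparisons with sample size of N=250 (N=75 for Aim 3) in the standard care group". Against this reference it sets 500 participants per intervention.

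On purpose, the introduction names "facilitated transitions of care to primary care clinicians for hypertension management" as one of three key programme components. Table 2, under care handoffs, gives the programme manager the task "Ensure that primary care or cardiology visits are scheduled at month 3", a parallel task for the 4-6 week postpartum visit, and reminders for all visits. Table 3 defines both attendance outcomes as having the visit. The Aim 1 analytic approach says that negative log-odds ratios mean improvement for binary outcomes, and it includes the health care utilization outcomes, where both attendance measures sit.

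**The concern.** For an outcome that is meant to rise, the useful sensitivity figure is the smallest increase the trial can detect. Table 6 gives the smallest decrease. A reader cannot recover one from the other by inverting it, because the limits are not symmetric on either ratio scale. A reader who wants to know how well the trial can judge its care-transition component therefore finds no answer in the table.

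The scale is a second problem. An odds ratio printed under a relative-risk title overstates the change in risk needed, and more so at a 40% baseline than at 10%.

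The Aim 1 sign rule carries the same direction error into the analysis. With attendance coded 1 for a visit, a successful programme gives a positive log-odds ratio, which the rule as written would call a worse outcome.

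**Working it through.** **Inputs.** Baselines of 10% and 40%, alpha 0.05 and 80% power come from Table 6. The group sizes n1 = 250 and n2 = 500 come from the power text. The documents do not state sidedness, so I take it as two-sided and check one-sided below.

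**Formula.** Pooled two-proportion z-test without continuity correction:

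- p̄ = (n1·p1 + n2·p2)/(n1 + n2)
- s0 = √[p̄(1 − p̄)(1/n1 + 1/n2)]
- s1 = √[p1(1 − p1)/n1 + p2(1 − p2)/n2]
- power = Φ[(|p1 − p2| − 1.96·s0)/s1]

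The limit is the p2 at which the bracket equals 0.84.

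**Reproducing the plan's figures (decreases).**

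- 10% to 4.52%: p̄ = 0.0635, s0 = 0.01889, s1 = 0.02113; (0.0548 − 0.0370)/0.02113 = 0.84. RR = 0.0452/0.10 = 0.45. OR = (0.0452/0.9548)/(0.10/0.90) = 0.426.
- 40% to 29.73%: p̄ = 0.3315, s0 = 0.03647, s1 = 0.03712; (0.1027 − 0.0715)/0.03712 = 0.84. RR = 0.2973/0.40 = 0.74. OR = (0.2973/0.7027)/(0.40/0.60) = 0.635.

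Table 6 prints 43% and 63%. This one method gives both, but only as odds ratios.

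**Other readings tried.**

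| Reading (250 v 500) | Result | Fits? |
|---|---|---|
| 43% as RR, 10% to 4.3% | power 0.83; 0.80 with continuity correction | 10% rows only, with correction |
| 63% as RR, 40% to 25.2% | power 0.98 | no |
| 43% as a relative increase, 10% to 14.3% | power 0.375 | no |
| RR 1/0.43, 10% to 23.3% | power 0.997 | no |
| OR 1/0.43, 10% to 20.5% | power 0.967 | no |
| 43% as the attendance rate itself | power about 1.00 | no |
| One-sided 0.05, decrease | OR 0.476 and 0.669 | no |

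With continuity correction the downward limits are RR 0.427 (OR 0.402) at 10% and RR 0.736 (OR 0.626) at 40%. That variant matches the table only if the 10% rows are relative risks and the 40% row is an odds ratio. No upward reading of 43% gives 80% power.

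**Detectable increases, same method.**

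- Primary care, 10% to 17.57%: s0 = 0.02769, s1 = 0.02549; (0.0757 − 0.0543)/0.02549 = 0.84. RR 1.76, OR 1.92.
- Postpartum visit, 40% to 50.79%: s0 = 0.03867, s1 = 0.03821; (0.1079 − 0.0758)/0.03821 = 0.84. RR 1.27, OR 1.55.

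**Range.** For primary care, two-sided variants of the test give 17.1% to 17.9% (RR 1.71 to 1.79). One-sided testing would give 16.6%. Other contrasts give 18.8% (250 v 250) and 16.0% (500 v 500). For the postpartum visit, those contrasts give 52.5% and 48.8%.

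**Effect on the severe hypertension figure.** If 43% is an odds ratio, the detectable rate is 4.52% and the risk reduction is 1 − 0.452, about 55%. Using the rounded OR of 0.43 gives 4.56%, or 54%. The text states 57%, which is 1 − 0.43 and thus a reduction in odds on this reading.

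**The case against.** The strongest reply is that little depends on these entries. Both attendance measures are secondary, the sample size follows from enrolment feasibility, and no decision rule uses the entries. A two-sided test detects a rise as well as a fall, whatever the table prints. All of that stands, and it limits the weight of the point. It does not make the entries right, because Table 6 is where the plan states its sensitivity for these outcomes.

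One could also suppose that the 10% is the share who miss the visit, so that a fall would be a benefit. The row label and the Table 3 definition both say attendance.

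Four stronger conclusions are tempting, and the documents do not support them:

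- *The primary care entry means 10% to 4.3%.* This follows from the title, but only a continuity-corrected test supports it, and that test does not fit the 40% row as a relative risk. The safe statement is a fall to about 4.3% to 4.6%.
- *The identical 43% shows a copying error.* Equal baselines and group sizes must give equal limits in the same direction.
- *The plan implies that attendance must more than double.* The plan never inverts the figure; 1/0.43 would be the reader's own construction.
- *The trial is underpowered for attendance.* The calculation shows 80% power for a rise of about 7.6 points from 10%.

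**Conclusion.** The point holds for both attendance rows. As printed, they are detectable decreases for outcomes that the programme's components and the manager's tasks are designed to increase. The relevant limits are about 17.6% from a 10% baseline and about 50.8% from 40%. These rest on 250 v 500, two-sided 0.05, a pooled test and no covariate adjustment, and they move with the contrast.

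That the binary entries are odds ratios is an inference. It is well supported, because one standard method gives both printed values on that scale and none of the variants tried gives both as relative risks, but the plan does not name its method. The restatement of the severe hypertension reduction as about 55% depends on that inference.

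The intended direction is read from the programme description and Table 2; the plan states no explicit directional hypothesis for attendance. The consequence is confined to the stated sensitivity for secondary outcomes, the wording of one primary-outcome figure, and the sign rule for reading the attendance models. The sample size and the models themselves are unaffected.

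**What to change.** 1. Confirm from the original calculation whether the binary entries in Table 6 are odds ratios or relative risks. Correct the title and column head accordingly and use one scale throughout.
2. Replace both attendance entries with detectable increases, given as absolute percentages with the ratio named: primary care 10% to about 17.6% (RR 1.76, OR 1.92); postpartum visit 40% to about 50.8% (RR 1.27, OR 1.55). Recompute both for whichever contrast is finally powered.
3. State the direction of benefit in each row.
4. If the odds-ratio reading is confirmed, restate the severe hypertension figure in the power text as about a 55% reduction in risk, or call the 57% a reduction in odds.
5. In the Aim 1 analytic approach, limit the rule that negative log-odds ratios mean improvement to outcomes where the event is undesirable, and say that for attendance a positive value is the improvement.

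The cost is a revised table and two or three edited sentences. Sample size, randomisation, data collection and models stay as they are.
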